### 7.2.1. Withdrawal of Consent

Participants who request to discontinue receipt of study intervention will remain in the study and must continue to be followed for protocol-specified follow-up procedures. The only exception to this is when a participant specifically withdraws consent for any further contact with him or her or persons previously authorized by the participant to provide this information. Participants should notify the investigator in writing of the decision to withdraw consent from future follow-up, whenever possible. The withdrawal of consent should be explained in detail in the medical records by the investigator, as to whether the withdrawal is only from further receipt of study intervention or also from study procedures and/or posttreatment study follow-up, and entered on the appropriate CRF page. In the event that vital status (whether the participant is alive or dead) is being measured, publicly available information should be used to determine vital status only as appropriately directed in accordance with local law.

### **7.3. Lost to Follow-Up**

A participant will be considered lost to follow-up if he or she repeatedly fails to return for scheduled visits and is unable to be contacted by the study site.

The following actions must be taken if a participant fails to return to the clinic for/attend a required study visit:

- The site must attempt to contact the participant and reschedule the missed visit as soon as possible. Counsel the participant on the importance of maintaining the assigned visit schedule, and ascertain whether the participant wishes to and/or should continue in the study;
- Before a participant is deemed lost to follow-up, the investigator or designee must make every effort to regain contact with the participant (where possible, 3 telephone calls and, if necessary, a certified letter or equivalent to the participant's last known mailing address or local equivalent methods). These contact attempts should be documented in the participant's medical record;
- Should the participant continue to be unreachable, he/she will be considered to have withdrawn from the study.

## **8. STUDY ASSESSMENTS AND PROCEDURES**

The investigator (or an appropriate delegate at the investigator site) must obtain a signed and dated ICD before performing any study-specific procedures.

The date of birth will be collected to critically evaluate the effect on growth by age. At a minimum the recorded date of birth must include the participant's month and year of birth.

Study procedures and their timing are summarized in the [SoA](#). Protocol waivers or exemptions are not allowed.

Safety issues should be discussed with the sponsor immediately upon occurrence or awareness to determine whether the participant should continue or discontinue study intervention.

Adherence to the study design requirements, including those specified in the [SoA](#), is essential and required for study conduct.

All screening evaluations must be completed and reviewed to confirm that potential participants meet all eligibility criteria. The investigator will maintain a screening log to record details of all participants screened and to confirm eligibility or record reasons for screening failure, as applicable.

Procedures conducted as part of the participant's routine clinical management (eg, blood count) and obtained before signing of the ICD may be utilized for screening or baseline purposes provided the procedures met the protocol-specified criteria and were performed within the time frame defined in the [SoA](#).

Every effort should be made to ensure that protocol-required tests and procedures are completed as described. However, it is anticipated that from time to time there may be circumstances outside the control of the investigator that may make it unfeasible to perform the test. In these cases, the investigator must take all steps necessary to ensure the safety and well-being of the participant. When a protocol-required test cannot be performed, the investigator will document the reason for the missed test and any corrective and preventive actions that he or she has taken to ensure that required processes are adhered to as soon as possible. The study team must be informed of these incidents in a timely manner.

For samples being collected and shipped, detailed collection, processing, storage, and shipment instructions and contact information will be provided to the investigator site prior to initiation of the study.

The total blood sampling volume for individual participants in this study is approximately 105 mL. The actual collection times of blood sampling may change. Additional blood samples may be taken for safety assessments at times specified by Pfizer.

Sampling volumes will not exceed 1% of total blood volume in any single blood draw or 3% blood volume within a 28-day period. [Ethical considerations for clinical trials on medicinal products conducted with minors. Recommendations of the expert group on clinical trials for the implementation of Regulation (EU) No 536/2014 on clinical trials on medicinal products for human use. Revision 1. 18 September 2017.].

If sampling will exceed these limits, then the samples should be prioritized as follows:

1. Clinical Safety Laboratory Samples.
2. PK.
3. Immunogenicity.
4. CCI [REDACTED].

Further details, such as minimum volumes required for each type of sample, can be found in the laboratory manual.

## **8.1. Efficacy Assessments**

### **8.1.1. Anthropometric Measurements**

Anthropometric measurements for height and proportionality will be performed and reported in the eCRF. Anthropometric measurements will be performed according to a trial-specific Anthropometric Measurement Manual, which will be provided to the investigational sites. This manual will contain a detailed description on the following:

- Which measurements to perform.
- The tools/instruments to be used.
- Standard procedure for performing these measurements.

The measurements to be taken on a 3-monthly basis are:

- Standing height (length for participants <2 years of age);
- Sitting height (crown-rump length for participants <2 years of age);
- Knee height;
- Head circumference;
- Arm span;
- Body weight;
- Elbow extension angle;
- Cranial dimensions (occipito-frontal, occipito-nasal distances).

Waist and chest circumference will be measured at baseline and at final visit.

Anthropometric data will only be collected by appropriately trained individuals at the trial site and in accordance with the anthropometric measurement manual. All sites will follow a consistent, structured and documented training program. This will occur prior to trial start, through regular refresher training and at targeted retraining based on analysis of measurement data consistency at the site.

Sites will be required to make all efforts to have the same anthropometrist at each visit for each participant (longitudinal consistency) and between participants (cross-sectional consistency). As well as following the specific procedures for measurement laid out in the measurement manual, sites will be provided with the same (or exactly equivalent) equipment across all sites and will follow the specific calibration procedures.

### 8.1.2. Polysomnography/Sleep Study

In participants with a documented current diagnosis of sleep disordered breathing prior to enrollment, baseline sleep study data will be collected. Baseline PSG data can be within 6 months prior to enrollment (this can be at site or a home study). The following data will be collected where available:

- Clinical summary of findings (including reported diagnosis);
- Whether study was performed in room air/oxygen/on continuous positive airway pressure;
- Apnea-hypopnea index (obstructive and total);
- Desaturation index (number of desaturations per hour >3% from baseline);
- Percentage time spent <90% oxygen saturation (SaO2);
- Percentage time spent with end-tidal carbon dioxide >50 mmHg;
- SaO2 nadir.

The sleep study will be repeated at 12 months and at the end of the study.

CCI [REDACTED]  
[REDACTED]

- [REDACTED]
- [REDACTED]
- [REDACTED]
- [REDACTED]
- [REDACTED]
- [REDACTED]
- [REDACTED]
- [REDACTED]

- CCI [REDACTED]

- [REDACTED]

- [REDACTED]

- [REDACTED]

- [REDACTED]

[REDACTED]

[REDACTED]

[REDACTED]

[REDACTED]

[REDACTED]

[REDACTED]

CCI

### **8.1.7. Acceptability and Tolerability Questionnaire - Achondroplasia**

The Acceptability and Tolerability Questionnaire – Achondroplasia will be used to measure the acceptability and tolerability of the SC injection being received as part of the achondroplasia treatment. There are 10 items with a recall period of ‘past 7 days’ that ask about pain, satisfaction with treatment, acceptability and tolerability of the injection. The caregiver completes the questionnaire throughout the study.

### **8.1.8. EQ-5D-Y and - (EQ-5D-Y Proxy Version 1**

The EQ-5D-Y is a newly developed generic instrument measuring health-related quality of life in children and adolescents 8 years and older. The EQ-5D-Y Proxy measures the health status of children 4 to 7 years of age. EQ-5D-Y was adapted from the EQ-5D original questionnaire (<http://www.euroqol.org/about-eq-5d.html>). It consists of a descriptive system (EQ-5D) of HRQoL states, consisting of 5 dimensions including mobility (walking about), self-care (looking after myself), usual activities (doing usual activities), pain/discomfort (having pain or discomfort), and anxiety/depression (feeling worried, sad or unhappy) each of which can take one of three responses. The responses record 3 levels of severity (no problems, some problems, or a lot of problems) within a particular EQ-5D dimension. Additionally, the EQ-5D consists of a standard vertical 20 cm visual analogue scale (EQ-VAS) for recording an individual’s rating of their current health-related quality of life state on a scale from 0 to 100 with 0 representing the worst and 100 the best health state he or she can imagine. All items refer to the health state “today”. For younger ages, the caregiver completes the EQ-5D-Y Proxy Version 1 and continues to complete throughout the study.

### **8.1.9. Tanner Staging**

In order to evaluate the effects of early puberty on growth trajectory, Tanner Stage of puberty will be assessed. For children 7 years of age and older, at the timing indicated in the SoA, the Tanner Stage of puberty will be recorded in the eCRF as stage I-V. Children under 7 years of age do not require this assessment, providing the investigator confirms there is no suspicion of a diagnosis of precocious puberty.

## **8.2. Safety Assessments**

Planned time points for all safety assessments are provided in the [SoA](#). Unscheduled clinical laboratory measurements may be obtained at any time during the study to assess any perceived safety issues.

### **8.2.1. Physical Examinations**

A complete physical examination will include, at a minimum, assessments of the cardiovascular, respiratory, gastrointestinal systems, and skin. Height and weight will also be measured and recorded as part of the anthropometric measurements collected.

Investigators should pay special attention to clinical signs related to previous serious illnesses.

Physical examination findings collected during the study will be considered source data and will not be required to be reported, unless otherwise noted. Any untoward physical examination findings that are identified during the active collection period and meet the definition of an AE or SAE ([Appendix 3](#)) must be reported according to the processes in [Sections 8.3.1 to 8.3.1.2](#).

### **8.2.2. Neurological Examination**

Neurological examination will be performed at visits indicated in the [SoA](#). This will include examination of cranial nerves (excluding fundoscopy) and examination of upper and lower limbs to include tone, power, reflexes and sensation. This should be performed by an investigator, or designee, experienced in such examinations in children who can suitably adapt to the age range in this study.

### **8.2.3. Vital Signs**

Oral, axillary, skin or temporal artery temperature, PR, respiratory rate, and BP will be assessed.

BP and PR measurements will be assessed with a completely automated device. Manual techniques will be used only if an automated device is not available. BP measurement must use an appropriate size cuff for the age and weight of the participant.

BP and PR measurements should be preceded by at least 5 minutes of rest for the participant in a quiet setting without distractions (eg, television, cell phones).

Vital signs (to be taken before blood collection for laboratory tests) will consist of 1 PR and 1 BP measurements. If the BP reading is abnormal then this should be repeated after 1 minute. Vital signs will be collected in the eCRF.

#### **8.2.4. Clinical Safety Laboratory Assessments**

See [Appendix 2](#) for the list of clinical safety laboratory tests to be performed and the [SoA](#) for the timing and frequency. All protocol-required laboratory assessments, as defined in [Appendix 2](#), must be conducted in accordance with the laboratory manual and the [SoA](#). Unscheduled clinical laboratory measurements may be obtained at any time during the study to assess any perceived safety issues.

The investigator must review the laboratory report, document this review, and record any clinically relevant changes occurring during the study in the AE section of the CRF. Clinically significant abnormal laboratory findings are those which are not associated with the underlying disease, unless judged by the investigator to be more severe than expected for the participant's condition.

All laboratory tests with values considered clinically significantly abnormal during participation in the study or within 1 week after the last dose of study intervention should be repeated until the values return to normal or baseline or are no longer considered clinically significant by the investigator or medical monitor.

If such values do not return to normal/baseline within a period of time judged reasonable by the investigator, the etiology should be identified, and the sponsor notified.

See [Appendix 5](#) for suggested actions and follow-up assessments in the event of potential drug-induced liver injury.

#### **8.2.5. Pregnancy Testing**

Pregnancy tests may be urine or serum tests but must have a sensitivity of at least 25 mIU/mL. Pregnancy tests will be performed in WOCBP at the times listed in the [SoA](#). Following a negative pregnancy test result at screening, appropriate contraception must be commenced, and second negative pregnancy test result will be required at the baseline visit prior to the participant's receiving the study intervention. Pregnancy tests will also be done whenever 1 menstrual cycle is missed during the active treatment period (or when potential pregnancy is otherwise suspected) and at the end of the study. Pregnancy tests may also be repeated if requested by IRBs/ECs or if required by local regulations. If a urine test cannot be confirmed as negative (eg, an ambiguous result), a serum pregnancy test is required. In such cases, the participant must be excluded if the serum pregnancy result is positive.

If a participant requiring pregnancy testing cannot visit a local laboratory, a home urine pregnancy testing kit with a sensitivity of at least 25 mIU/mL may be used by the participant to perform the test at home, if compliant with local regulatory requirements. The pregnancy test outcome should be documented in the participant's source documents/medical records and relevant data recorded on the CRF. Confirm that the participant is adhering to the contraception method(s) required in the protocol.

Contraception check is applicable to both WOCBP and sexually active male participants.

### **8.2.6. Suicidal Ideation and Behavior Risk Monitoring**

Not Applicable.

### **8.3. Adverse Events, Serious Adverse Events, and Other Safety Reporting**

The definitions of an AE and an SAE can be found in [Appendix 3](#).

AEs may arise from symptoms or other complaints reported to the investigator by the participant (or, when appropriate, by a caregiver, surrogate, or the participant's legally authorized representative), or they may arise from clinical findings of the investigator or other healthcare providers (clinical signs, test results, etc.).

The investigator and any qualified designees are responsible for detecting, documenting, and recording events that meet the definition of an AE or SAE and remain responsible to pursue and obtain adequate information both to determine the outcome and to assess whether the event meets the criteria for classification as an SAE or caused the participant to discontinue the study intervention (see [Section 7.1](#)).

During the active collection period as described in [Section 8.3.1](#), each participant/parent/legal guardian/legally authorized representative will be questioned about the occurrence of AEs in a nonleading manner.

In addition, the investigator may be requested by Pfizer Safety to obtain specific follow-up information in an expedited fashion.

#### **8.3.1. Time Period and Frequency for Collecting AE and SAE Information**

The time period for actively eliciting and collecting AEs and SAEs (“active collection period”) for each participant begins from the time the participant provides informed consent, which is obtained before the participant’s participation in the study (ie, before undergoing any study-related procedure and/or receiving study intervention), through and including a minimum of 28 calendar days, except as indicated below, after the last administration of the study intervention.

Follow-up by the investigator continues throughout and after the active collection period and until the AE or SAE or its sequelae resolve or stabilize at a level acceptable to the investigator.

For participants who are screen failures, the active collection period ends when screen failure status is determined.

If the participant withdraws from the study and also withdraws consent for the collection of future information, the active collection period ends when consent is withdrawn.

If a participant permanently discontinues or temporarily discontinues study intervention because of an AE or SAE, the AE or SAE must be recorded on the CRF and the SAE reported using the CT SAE Report Form.

Investigators are not obligated to actively seek information on AEs or SAEs after the participant has concluded study participation. However, if the investigator learns of any SAE, including a death, at any time after a participant has completed the study, and he/she considers the event to be reasonably related to the study intervention, the investigator must promptly report the SAE to Pfizer using the CT SAE Report Form.

#### **8.3.1.1. Reporting SAEs to Pfizer Safety**

All SAEs occurring in a participant during the active collection period as described in [Section 8.3.1](#) are reported to Pfizer Safety on the CT SAE Report Form immediately upon awareness and under no circumstance should this exceed 24 hours, as indicated in [Appendix 3](#). The investigator will submit any updated SAE data to the sponsor within 24 hours of it being available.

#### **8.3.1.2. Recording Nonserious AEs and SAEs on the CRF**

All nonserious AEs and SAEs occurring in a participant during the active collection period, which begins after obtaining informed consent as described in [Section 8.3.1](#), will be recorded on the AE section of the CRF.

The investigator is to record on the CRF all directly observed and all spontaneously reported AEs and SAEs reported by the participant.

Reporting of AEs and SAEs for participants who fail screening are subject to the CRF requirements as described in [Section 5.4](#).

#### **8.3.2. Method of Detecting AEs and SAEs**

The method of recording, evaluating, and assessing causality of AEs and SAEs and the procedures for completing and transmitting SAE reports are provided in [Appendix 3](#).

Care will be taken not to introduce bias when detecting AEs and/or SAEs. Open-ended and nonleading verbal questioning of the participant is the preferred method to inquire about AE occurrences.

#### **8.3.3. Follow-Up of AEs and SAEs**

After the initial AE or SAE report, the investigator is required to proactively follow each participant at subsequent visits/contacts. For each event, the investigator must pursue and obtain adequate information until resolution, stabilization, the event is otherwise explained, or the participant is lost to follow-up (as defined in [Section 7.3](#)).

In general, follow-up information will include a description of the event in sufficient detail to allow for a complete medical assessment of the case and independent determination of possible causality. Any information relevant to the event, such as concomitant medications and illnesses, must be provided. In the case of a participant death, a summary of available autopsy findings must be submitted as soon as possible to Pfizer Safety.

Further information on follow-up procedures is given in [Appendix 3](#).

#### **8.3.4. Regulatory Reporting Requirements for SAEs**

Prompt notification by the investigator to the sponsor of an SAE is essential so that legal obligations and ethical responsibilities toward the safety of participants and the safety of a study intervention under clinical investigation are met.

The sponsor has a legal responsibility to notify both the local regulatory authority and other regulatory agencies about the safety of a study intervention under clinical investigation. The sponsor will comply with country-specific regulatory requirements relating to safety reporting to the regulatory authority, IRBs/ECs, and investigators.

Investigator safety reports must be prepared for SUSARs according to local regulatory requirements and sponsor policy and forwarded to investigators as necessary.

An investigator who receives SUSARs or other specific safety information (eg, summary or listing of SAEs) from the sponsor will review and then file it along with the SRSD(s) for the study and will notify the IRB/EC, if appropriate according to local requirements.

#### **8.3.5. Environmental Exposure, Exposure During Pregnancy or Breastfeeding, and Occupational Exposure**

Environmental exposure, occurs when a person not enrolled in the study as a participant receives unplanned direct contact with or exposure to the study intervention. Such exposure may or may not lead to the occurrence of an AE or SAE. Persons at risk for environmental exposure include healthcare providers, family members, and others who may be exposed. An environmental exposure may include EDP, EDB, and occupational exposure.

Any such exposure to the study intervention under study are reportable to Pfizer Safety within 24 hours of investigator awareness.

##### **8.3.5.1. Exposure During Pregnancy**

An EDP occurs if:

- A female participant is found to be pregnant while receiving or after discontinuing study intervention.
- A male participant who is receiving or has discontinued study intervention exposes a female partner prior to or around the time of conception.
- A female is found to be pregnant while being exposed or having been exposed to study intervention due to environmental exposure. Below are examples of environmental EDP:

- A female family member or healthcare provider reports that she is pregnant after having been exposed to the study intervention by ingestion, inhalation, or skin contact.
- A male family member or healthcare provider who has been exposed to the study intervention by ingestion, inhalation, or skin contact then exposes his female partner prior to or around the time of conception.

The investigator must report EDP to Pfizer Safety within 24 hours of the investigator's awareness, irrespective of whether an SAE has occurred. The initial information submitted should include the anticipated date of delivery (see below for information related to termination of pregnancy).

- If EDP occurs in a participant or a participant's partner, the investigator must report this information to Pfizer Safety on the CT SAE Report Form and an EDP Supplemental Form, regardless of whether an SAE has occurred. Details of the pregnancy will be collected after the start of study intervention and until 4 weeks after the last dose.
- If EDP occurs in the setting of environmental exposure, the investigator must report information to Pfizer Safety using the CT SAE Report Form and EDP Supplemental Form. Since the exposure information does not pertain to the participant enrolled in the study, the information is not recorded on a CRF; however, a copy of the completed CT SAE Report Form is maintained in the investigator site file.

Follow-up is conducted to obtain general information on the pregnancy and its outcome for all EDP reports with an unknown outcome. The investigator will follow the pregnancy until completion (or until pregnancy termination) and notify Pfizer Safety of the outcome as a follow-up to the initial EDP Supplemental Form. In the case of a live birth, the structural integrity of the neonate can be assessed at the time of birth. In the event of a termination, the reason(s) for termination should be specified and, if clinically possible, the structural integrity of the terminated fetus should be assessed by gross visual inspection (unless preprocedure test findings are conclusive for a congenital anomaly and the findings are reported).

Abnormal pregnancy outcomes are considered SAEs. If the outcome of the pregnancy meets the criteria for an SAE (ie, ectopic pregnancy, spontaneous abortion, intrauterine fetal demise, neonatal death, or congenital anomaly in a live-born baby, a terminated fetus, an intrauterine fetal demise, or a neonatal death), the investigator should follow the procedures for reporting SAEs. Additional information about pregnancy outcomes that are reported to Pfizer Safety as SAEs follows:

- Spontaneous abortion including miscarriage and missed abortion;

- Neonatal deaths that occur within 1 month of birth should be reported, without regard to causality, as SAEs. In addition, infant deaths after 1 month should be reported as SAEs when the investigator assesses the infant death as related or possibly related to exposure to the study intervention.

Additional information regarding the EDP may be requested by the sponsor. Further follow-up of birth outcomes will be handled on a case-by-case basis (eg, follow-up on preterm infants to identify developmental delays). In the case of paternal exposure, the investigator will provide the participant with the Pregnant Partner Release of Information Form to deliver to his partner. The investigator must document in the source documents that the participant was given the Pregnant Partner Release of Information Form to provide to his partner.

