**5.3. Lifestyle Considerations**

**5.3.1. Contraception**

Participants that become a WOCBP (defined as reaching menarche) during the course of the study, the investigator or his or her designee, in consultation with the participant, will confirm that the participant has been informed of the potential risks of pregnancy whilst receiving study intervention and advised of the need for continuing total abstinence from sexual activity (see [Appendix 4 Section 10.4.4](#)). At time points indicated in the SoA, the investigator or designee will inform the participant of the need to use continue total abstinence from sexual activity and document the conversation and the participants affirmation in the participants' chart. This also applies to males should they become sexually active. In addition, the investigator or designee will instruct the participant to call immediately if total abstinence from sexual activity is discontinued or if pregnancy is known or suspected in the participant or partner.

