## **10.4. Appendix 4: Contraceptive and Barrier Guidance**

### **10.4.1. Male Participant Reproductive Inclusion Criteria**

Male participants are eligible to participate if they agree to the following requirements during the intervention period and for at least 111 days after the last dose of study intervention, which corresponds to the 21 days time needed to eliminate reproductive safety risk of the study intervention(s) *plus* an additional 90 days (a spermatogenesis cycle):

- Be abstinent from heterosexual intercourse as their preferred and usual lifestyle (abstinent on a long term and persistent basis) and agree to remain abstinent.

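### The single 4-week limit on collecting pregnancy details (Protocol 8.3.5.1) ends at least 83 days before the protocol's own male risk period; known pregnancies remain reportable, so the impact is low

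*Protocol*

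**What the plan says.** Protocol Section 8.3.5.1 defines exposure during pregnancy. For males the definition is: "A male participant who is receiving or has discontinued study intervention exposes a female partner prior to or around the time of conception". It has no end date and expressly includes males who have stopped the drug.

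The reporting duty follows: "The investigator must report EDP to Pfizer Safety within 24 hours" of becoming aware, whether or not a serious adverse event has occurred. The next bullet covers pregnancies in a participant or in a participant's partner. It names the forms to use and closes with the limit: "Details of the pregnancy will be collected after the start of study intervention and until 4 weeks after the last dose". No separate limit for partners appears there or elsewhere in the protocol. Later in the same section, every reported pregnancy is to be followed to completion or termination.

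Section 10.4.1 sets the male abstinence period: the intervention period and "for at least 111 days after the last dose of study intervention". It builds this from 21 days for the drug's reproductive risk to clear and 90 days for a cycle of sperm production. Section 10.4.2 sets 28 days for female participants.

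Section 5.3.1 has participants, including males who become sexually active, told to "call immediately if total abstinence from sexual activity is discontinued or if pregnancy is known or suspected in the participant or partner". It gives no end date for that instruction.

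**The concern.** The 4-week limit equals the female post-dose period but is applied to partners of male participants as well. The protocol treats a male participant as a possible source of reproductive risk for at least 111 days after dosing. A partner pregnancy conceived between days 29 and 111 lies inside that period but outside the stated collection limit. A site working from this sentence could reasonably stop asking about partners at day 28.

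The sentence also sits awkwardly in its own section. Reporting runs from awareness and follow-up runs to outcome, yet the collection of details is said to stop at 4 weeks.

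What is at stake is safety information. Section 4.2 says that human reproductive safety data are lacking, and Section 4.2.4 that developmental toxicity has not been studied, although Section 4.2 also finds no ground in the pharmacology to suspect teratogenicity. The trial's endpoints are not involved.

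**Working it through.** **Inputs**
- Collection limit, participants and partners: 4 weeks (8.3.5.1).
- Male period: at least 111 days, from 21 days and 90 days (10.4.1).
- Female period: 28 days (10.4.2).

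**Reproducing the plan's figure**
21 + 90 = 111 days, as Section 10.4.1 states.

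**The gap**
- Limit in days: 4 × 7 = 28.
- Partners of male participants: 111 − 28 = 83 days. This is a minimum, because 111 is itself a minimum.
- Female participants: 28 − 28 = 0 days between the two stated periods.

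**Sensitivity to the clearance time**
Section 10.4.1 uses 21 days for the drug's reproductive risk to clear; Section 10.4.2 uses 28 days for the same purpose. With 28 days the male period would be 28 + 90 = 118 days and the gap 118 − 28 = 90 days. The gap is therefore at least 83 days as written, and 90 days if the female clearance time were used for both sexes.

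**Three readings of the limit**
1. *All gathering of pregnancy details stops at 4 weeks.* This conflicts with follow-up to outcome in the same section, for participants and partners alike.
2. *Only pregnancies detected within 4 weeks are collected.* This is compatible with follow-up to outcome. It is still at least 83 days short for partners, and it sits badly with a reporting duty triggered by awareness at any time.
3. *Only pregnancies conceived within 4 weeks are collected.* This suits female participants. It is still at least 83 days short for partners.

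No reading brings the limit into line with the male period.

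**Expected number of events**
Participants are at most 12 years old at entry (5.1) and are treated for up to 24 months (4.1), so the oldest are about 12 + 2 = 14 years at the end of treatment. Abstinence is the required method, with alternatives only in Italy, where the duration of contraception is unchanged (10.6.1.4). The documents give no pregnancy rate and none is assumed here; the number should be very small.

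**The case against.** The strongest case against the point is that the duties that matter have no 4-week end. The exposure definition reaches males who have stopped treatment, reporting runs from awareness, follow-up runs to outcome, and abnormal outcomes count as serious adverse events. Section 8.3.1 adds that a serious event must be reported if the investigator learns of it "at any time after a participant has completed the study, and he/she considers the event to be reasonably related to the study intervention". The instruction to call in 5.3.1 is triggered by a break in abstinence, and male abstinence runs to at least day 111, so the two sections together can be read as carrying it that far. The schedule of activities also appears to mark a contraception check at the follow-up contact, and its footnotes apply that check to sexually active males.

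Most of this stands and sets the size of the point. It does not remove the mismatch. The awareness-based duty works only if someone tells the site. The rule in 8.3.1 requires the investigator to judge the event related, and would not by itself reach an uncomplicated pregnancy. The day-111 reading of 5.3.1 is an inference; no section states it.

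A second objection also stands: the 111 and 28 days are abstinence periods, that is, windows for conception, while the 4 weeks concern the collection of details. Pregnancies are recognised some time after conception. Two stronger inferences therefore fail:
- A reader might take 28/111 = 25.2% as the share of partner pregnancies that would be captured. It is a ratio of two stated periods; later pregnancies that become known must still be reported.
- A reader might take the zero-day difference for female participants as showing that the limit is sound for them. A conception shortly before day 28 would usually be recognised after the limit. For the same reason, simply moving the partner limit to a day-111 detection cut-off would not be enough.

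**Conclusion.** The point holds as a low-impact inconsistency in safety collection. For partners of male participants, the stated limit ends at least 83 days before the protocol's own male risk period, and it fits poorly with the open-ended reporting and follow-up duties beside it.

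A reader might infer that partner pregnancies go unreported for 83 days. The documents do not support that, because any pregnancy that becomes known must be reported within 24 hours and followed to outcome. What is unclear is how long sites should keep asking and collecting.

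The conclusion rests on taking the 111 days in 10.4.1 as the sponsor's intended male risk period, and on the limit applying to partners because it sits in the bullet that names them. It does not depend on any assumed pregnancy rate. No endpoint, estimand or planned analysis changes.

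**What to change.** At the next protocol amendment, replace the closing sentence of that bullet in 8.3.5.1 with a rule defined by conception. Details are collected for any pregnancy conceived from the first dose until 28 days after the final dose in a female participant, or until at least 111 days after the final dose in the partner of a male participant. The rule applies whenever the pregnancy becomes known, and every reported pregnancy is followed to outcome. The last two clauses keep day 28 or day 111 from being read as a cut-off for detection or reporting.

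Use the contraception check at the existing phone follow-up to tell male participants and their caregivers that the 5.3.1 instruction to call runs through day 111.

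The cost is one line in an amendment, a reminder at a contact already planned, and a longer passive reporting window. No visit or sample is added. An amendment needs ethics approval before changes are implemented (10.1.1), so the wording should go into the next planned amendment; the size of the issue does not warrant a separate one.
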